8.3 Other Efficacy Analysis

All subjects who have repeat plaque (TPI) assessments (conducted by the examiner) form the repeatability population which will be used for repeatability analysis. The repeat assessments will be compared to the original assessments. The repeat assessments will not be used in any efficacy analysis. The first and second assessments on each tooth at a given visit will be cross-tabulated and a weighted Kappa coefficient (κ) will be calculated, along with the 95% confidence interval, to assess the intra-examiner repeatability. Repeatability will be deemed:

- Excellent, if $\kappa > 0.75$
- Fair to good, if $0.4 \leq \kappa \leq 0.75$
- Poor if $\kappa < 0.4$

All subjects who have repeatability data will be included in this analysis.

9 Safety Analysis

The safety profile of the study treatments will be assessed with respect to adverse events (AEs). Oral soft tissue (OST) abnormalities are included as AEs if they appear or worsen after the initial assessment. All safety data will be reported for the Safety population as per treatment received (using variable ATRT). All AEs will be reviewed by the Clinical Research Director or Scientist prior to database lock and unblinding and will be coded using the Medical Dictionary for Regulatory Activities

 GlaxoSmithKline	Document Name	206886 SAP		
	Type	Version	Document Identifier	Effective Date
	eldo_clinical_doc	1.0; CURRENT; Most-Recent; Effective	090032d580cd9b2d	04-Jan-2017 09:07:54
	Reason For Issue	Auto Issue		

(MedDRA). During this review stage, AEs will be further categorized as oral or non-oral. AEs will be regarded as treatment emergent if they occur on or after the start time of the first treatment application (as determined by EXSTDT and EXSTTM from the EXPOSURE panel if this date is missing a suitable alternative will be used eg date and time of randomisation). All other AEs prior to this will be considered non-treatment emergent. The following summary tables and listings will be presented by treatment group.

- Table of treatment emergent AEs by Oral/Non-Oral and Preferred Term
- Table of treatment emergent AEs by SOC and Preferred Term
- Treatment emergent treatment related AEs by Oral/Non-Oral and Preferred Term
- Listing of all AEs (including Non-treatment emergent).
- Listing of serious AEs. (if there are none, a null listing will be produced)

No inferential analyses will be performed to compare treatments with respect to safety.

10 Interim Analysis

There is no interim analysis planned for this study.

11 Topline Summary

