4. DENTAL HEALTH

A. Good dental health based on medical history and oral soft tissue examination at screening.
 
B. A minimum of 20 permanent gradable teeth. (Gradable teeth are those where restorative materials cover less than 25% of the tooth surface to be graded).
 
C. Mean Turesky plaque score of ≥ 2.00 at Visit 1 and Visit 2 (pre-brushing plaque assessment).

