5.1 Analysis Populations

Safety population is defined as all subjects who are randomized and have received at least one dose of study products.

The intent to treat (ITT) population is defined as those subjects who are randomized, receive at least one dose of study product and have at least one post-baseline efficacy measurement.

The Per Protocol (PP) population will be a subset of the ITT population. Subjects with a protocol violation that is deemed to affect efficacy for all efficacy assessments will be excluded from the PP population. Subjects with a protocol violation that is deemed to affect efficacy for only some (but not all) of the efficacy assessments will be part of the PP population, but their data will be excluded from the assessment at which the protocol violation occurred. Efficacy analysis will be based on ITT population. A PP analysis will be performed only if 10% or more ITT subjects are excluded from PP population.

The repeatability population is defined as all subjects who have a repeat clinical assessment (TPI) at any visit.

Any of the following will be considered a protocol violation which will warrant exclusion from efficacy analysis:

- Violation of inclusion or exclusion criteria that are deemed to affect efficacy.
- Medical history which is deemed to affect efficacy.
- Use of prohibited treatment or medication before or during the study, which is felt to affect the assessment of efficacy.

 GlaxoSmithKline	Document Name	206886 SAP		
	Type	Version	Document Identifier	Effective Date
	eldo_clinical_doc	1.0; CURRENT; Most-Recent; Effective	090032d580cd9b2d	04-Jan-2017 09:07:54
	Reason For Issue	Auto Issue		

- Not receiving randomized treatment.
- Noncompliance on treatment washout

Further data listings will be included in the review of protocol violations but will be reviewed on a case-by-case basis to determine whether the data should be excluded from a PP. Full data listings will be provided in review listing requirement document.

Protocol violations which warrant exclusion from efficacy analysis will be identified between the statistician and medical director or designee, ahead of database lock and breaking the study blind.

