**P-value for test products against two controls will be provided only if Pos.Control vs neg.Control is significant.

[1] From ANCOVA analysis for change from pre-brushing with treatment and period as fixed effect, subject as random effect, subject-level baseline and period-level minus subject-level baseline as covariates.

[2] Difference is first named treatment minus second named treatment such that a negative difference favors the first named treatment

(Page X of Y)

PPD

PPD

 GlaxoSmithKline	Document Name	206886 SAP		
	Type	Version	Document Identifier	Effective Date
	eldc_clinical_doc	1.0: CURRENT: Most-Recent: Effective	090032d580cd9b2d	04 Jan 2017 09:07:54
	Reason For Issue	Auto Issue		

	Document Name	206886 SAP	
	Type	Version	Document Identifier
	eldo_clinical_doc	1.0: CURRENT: Most-Recent: Effective	090032d580cd9b2d
	Reason For Issue	Auto Issue	
			Effective Date
			04 Jan 2017 09:07:54

Protocol: 206886

Program Run Date: ddmonyyyy

Table 9.3.2
 Repeatability Analysis of Turesky Plaque Index
 Repeatability Population

Study Population: Repeatability (N=xx)

First Assessment [1]	Second Assessment					
	Missing	0	1	2	3	4
MISSING	XX	XX	XX	XX	XX	XX
0	XX	XX (xx.x%)				
1	XX	XX (xx.x%)				
2	XX	XX (xx.x%)				
3	XX	XX (xx.x%)				
4	XX	XX (xx.x%)				

WEIGHTED KAPPA = 0.xxx

95% C.I. = 0.xxx, 0.xxx

Note: Percentages are based on total of all non-missing combinations

[1] The first assessment is the one used in the efficacy analysis.

0: No plaque

1: Slight flecks of plaque at the cervical margin of the tooth

2: A thin continuous band of plaque (1 mm or smaller) at the cervical margin of the tooth

3: A band of plaque wider than 1 mm but covering less than 1/3 of the crown of the tooth

4: Plaque covering at least 1/3 but less than 2/3 of the crown of the tooth

5: Plaque covering 2/3 or more of the crown of the tooth

(Page X of Y)

PPD

PPD

[figure not shown]
	Document Name	206886 SAP		
	Type	Version	Document Identifier	Effective Date
	eldo_clinical_doc	1.0: CURRENT, Most-Recent, Effective	090032d4580cd9b2d	04 Jan 2017 09:07:54
	Reason For Issue	Auto Issue		

Protocol: 206886

Program Run Date: DDMMYYYY

Figure 9.1
 Mean TPI change from pre-brushing (\pm SE) by treatment
 ITT Population

Study Population: ITT (N=xxx)

PPD

PPD

[figure not shown]
	Document Name	206886 SAP	
	Type	Version	Document Identifier
	eldo_clinical_doc	1.0: CURRENT: Most-Recent: Effective	090032d580cd9b2d
	Reason For Issue	Auto Issue	
			Effective Date

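### Repeatability kappa: a 95% CI taken from one pooled table of tooth or surface pairs ignores clustering within mouths and is too narrow if agreement is correlated within a mouth

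*SAP*

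**What the plan says.** SAP 8.3 (repeated in Protocol 9.3.5) states: "The first and second assessments on each tooth at a given visit will be cross-tabulated and a weighted Kappa coefficient" is to be calculated, "along with the 95% confidence interval, to assess the intra-examiner repeatability". Kappa is then labelled Excellent above 0.75, Fair to good from 0.4 to 0.75, and Poor below 0.4. The same section adds: "The repeat assessments will not be used in any efficacy analysis".

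The shell for Table 9.3.2 (SAP Appendix 3) shows a single cross-tabulation ending in "WEIGHTED KAPPA = 0.xxx" and "95% C.I. = 0.xxx, 0.xxx". Its footnotes cover the percentage base, which assessment feeds the efficacy analysis, and the grade labels. They do not say how the interval is obtained.

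On who contributes, SAP 5.1 says: "The repeatability population is defined as all subjects who have a repeat clinical assessment (TPI) at any visit". Protocol 3.1 lists repeatability after both the pre-brushing and the post-brushing assessment at each treatment visit. One person can therefore enter the table more than once.

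On pairs per mouth, Protocol 4.1 (criterion 4B) requires: "A minimum of 20 permanent gradable teeth". Protocol 6.2.3 excludes wisdom teeth, divides each tooth into six areas and records a grade for each surface.

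Neither document gives a variance method for kappa, treats the subject as a cluster, or names the kappa weights.

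**The concern.** The cross-tabulation drops the subject identifier. Once the pairs are in it, an interval computed from it can only use the total number of pairs as its sample size. Those pairs come in blocks from one mouth, scored twice by one examiner in one session. Mouths differ in plaque level and probably in how hard they are to score, and the examiner may be slightly more lenient or strict on one pass. Each of these makes pairs from one mouth resemble each other, so the effective sample is smaller than the pair count.

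What is at stake is the stated precision of examiner repeatability. Protocol 3.4 uses repeat assessments to support its single-examiner design, and this kappa is the only planned analysis of them. A printed 95% interval should cover close to 95% of the time.

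**Working it through.** **Figures in the plan.** None is given for kappa or its interval, so there is nothing to reproduce. The plan's power calculation is unrelated.

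**Pairs per mouth.** At least 20 teeth (Protocol 4.1). At most 32 − 4 = 28, assuming full dentition without wisdom teeth. Six areas per tooth (Protocol 6.2.3) give 20 × 6 = 120 to 28 × 6 = 168 surfaces.

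**Rough size by design effect.** The interval should be wider by √(1 + (m − 1)ρ), where m is pairs per mouth and ρ the within-mouth correlation. The documents give no ρ; 0.01 to 0.20 is assumed.

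- m = 20, ρ = 0.01: √1.19 = 1.09
- m = 28, ρ = 0.20: √6.40 = 2.53
- m = 120, ρ = 0.01: √2.19 = 1.48
- m = 168, ρ = 0.20: √34.4 = 5.87

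**Simulation of kappa.** Assumed: 20 subjects with one repeat each; 24 tooth or 24 × 6 = 144 surface pairs; latent score with mean 2.5, site SD 0.9 and scoring-error SD 0.5, cut to grades 0 to 5; linear weights; 600 runs per row. Subject SD is the spread of plaque level between mouths. Shift SD is a whole-mouth shift at the second scoring. κ = (p_o − p_e)/(1 − p_e), with weighted observed and expected agreement. The independent-pairs SE is the usual large-sample one. The jackknife SE is √[((S − 1)/S) Σ(κ₍₋ₛ₎ − mean)²], used with a t quantile on S − 1 degrees of freedom, S being the number of subjects.

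| Pairs per mouth | Subject SD / shift SD | κ | True SE | Independent-pairs SE | Ratio | Coverage, independent pairs | Coverage, jackknife |
|---|---|---|---|---|---|---|---|
| 24 | 0 / 0 | 0.516 | 0.0261 | 0.0257 | 1.01 | 94.5% | 94.3% |
| 24 | 0.4 / 0 | 0.548 | 0.0260 | 0.0245 | 1.06 | 94.0% | 95.5% |
| 24 | 0.4 / 0.2 | 0.534 | 0.0275 | 0.0248 | 1.11 | 91.3% | 93.7% |
| 24 | 0.6 / 0.3 | 0.553 | 0.0327 | 0.0238 | 1.38 | 84.8% | 95.2% |
| 144 | 0 / 0 | 0.516 | 0.0103 | 0.0105 | 0.98 | 95.2% | 95.5% |
| 144 | 0.4 / 0 | 0.549 | 0.0139 | 0.0100 | 1.39 | 83.8% | 94.2% |
| 144 | 0.4 / 0.2 | 0.535 | 0.0149 | 0.0101 | 1.47 | 81.5% | 95.3% |
| 144 | 0.6 / 0.3 | 0.554 | 0.0232 | 0.0097 | 2.39 | 61.5% | 93.5% |

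With 40 subjects the ratios were 1.00 to 1.32 (24 pairs) and 0.99 to 2.40 (144 pairs). Differences in plaque level between mouths alone (shift SD 0) already gave 1.36 to 1.39 for surfaces.

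**Wider assumptions.** A second set of runs let scoring error also vary between subjects (mean 2.6, subject SD 0.4, site SD 0.7 or 1.0, error SD 0.45, shift SD 0 to 0.3, linear and quadratic weights).

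- One repeat per subject, 20 or 30 subjects: ratio 1.05 to 1.65 for teeth and 1.24 to 3.40 for surfaces. Coverage fell to 74% and 42%.
- Two repeats per subject, 20 subjects: 1.07 to 2.13 for teeth and 1.45 to 4.42 for surfaces. Coverage fell to 67% and 33%.
- No clustering: 1.02 to 1.09.
- Jackknife coverage in the main runs: 91.5% to 97.2%.

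**One kappa per visit.** The text of SAP 8.3 could be read this way, although the shell shows one table. With 8 or 12 subjects the ratios were 1.07 to 1.61 for teeth and 1.25 to 3.27 for surfaces, so clustering remains.

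**The case against.** The case against is mostly about weight. The documents never say that an independent-pairs variance will be used. Too narrow an interval also needs positive within-mouth dependence, and without it the usual interval is sound. Every size above rests on chosen inputs; the documents give only a target of two repeat subjects per assessment day. The labels use kappa, not its interval. Even the widest corrected half-width for surfaces in the main runs, 0.082, is small beside the Fair to good band of 0.75 − 0.40 = 0.35.

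All of that stands, and it limits the point without removing it. The shell puts every pair in one table without subjects, and nothing else in either document supplies a correction.

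Some stronger readings are tempting but not supported:

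- A reader might infer that the interval is certain to be badly wrong. The documents do not quantify the dependence, and for tooth pairs with weak dependence the error was about 3% to 6%.
- A reader might infer that kappa itself, or the efficacy result, is compromised. Clustering does not bias kappa, and the repeats enter no efficacy analysis.
- A reader might infer that the unnamed weights make the label unreliable. They can change it under some inputs. At error SD 0.45, linear and quadratic kappa were 0.514 and 0.695 with site SD 0.7 (same label) but 0.618 and 0.799 with site SD 1.0 (different labels). In the first case, putting half the repeats at an assumed post-brushing mean of 1.6 gave 0.576 and 0.758, which also differ. This is a reason to name the weights; it does not show how likely a different label is.
- A reader might infer that grade 5 was left out of the analysis. As read, the header and rows of Table 9.3.2 stop at 4, but the table text is partly broken and its legend includes "5: Plaque covering 2/3 or more of the crown of the tooth". It is something to check.

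**Conclusion.** The concern holds as a minor, conditional point. A 95% interval computed from the pooled table of SAP 8.3 and Table 9.3.2 treats 20 to 28 tooth pairs or 120 to 168 surface pairs per mouth as independent. It overstates precision if agreement is positively correlated within mouths. That is likely when one examiner scores the same mouth twice in one session, but its strength is unknown. Under the assumed inputs the shortfall is negligible for teeth with weak dependence and roughly 2 to 3 fold or more for surfaces with strong dependence. Confidence is high in the gap and its direction, and low in any single figure for its size. The effect is confined to one descriptive table.

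**What to change.** Add to SAP 8.3: *The 95% confidence interval for kappa will be obtained by a jackknife that leaves out one subject at a time, removing all pairs and all repeat examinations of that subject together, with a t quantile on the number of subjects minus one degrees of freedom.* A bootstrap that resamples subjects would serve equally well. The protocol need not change for this, since Protocol 9.3 leaves such detail to the SAP.

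The cost is a short macro and a wider interval. In the main runs of the second set it widened by 1.09 to 2.05 times for teeth and 1.32 to 4.40 times for surfaces. If kappa is reported per visit, few subjects make the jackknife less exact: coverage was 89% to 98% with 8 or 12.

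Three clarifications belong with this edit, though none would justify a comment alone:

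- State whether the pair is the tooth or the tooth surface. Protocol 9.3.5 and SAP 8.3 name the tooth, while Protocol 6.2.3 grades each surface and defines no tooth-level grade. Either choice is open. Pairing by tooth needs a rule for combining six grades; pairing by surface should be recorded as a departure from Protocol 9.3.5.
- Name the kappa weights. This and the pairing unit should be settled before the repeat data are seen.
- Check that the Table 9.3.2 shell has a row and a column for grade 5.

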11.1 Variables for topline

Efficacy

TPI score change from pre-brushing after a single brushing treatment. Both primary comparison and secondary comparisons will be provided.

Safety

Adverse events

11.2 Outputs for topline

	Document Name	206886 SAP		
	Type	Version	Document Identifier	Effective Date
	eldo_clinical_doc	1.0; CURRENT; Most-Recent; Effective	090032d580cd9b2d	04-Jan-2017 09:07:54
	Reason For Issue	Auto Issue		

Datasets/Tables	Description
Datasets	PONNFL, POPNEXCL, RANDOM ADSL, ADAE, ADTPI, STAT1, STAT2
Tables – Efficacy	No efficacy tables required if information can be obtained directly from stats datasets otherwise define here
Tables Safety	9.4.1 – Listing Of Adverse Events  Safety Population If there are <10 AEs the listing will be enough else:- 9.4.2 – Summary Of Treatment Emergent Adverse Events  Safety Population
Figures	Generated from data from stats datasets
Non priority outputs	Table 9.1.1 – Subject Disposition

12 Changes to Planned Analysis

There is no change to the planned analysis.

13 References

GSKCH clinical study RH01445 Plaque Removal Efficacy of Four Dentifrices in a Single Brushing Model.

 GlaxoSmithKline	Document Name	206886 SAP		
	Type	Version	Document Identifier	Effective Date
	eldc_clinical_doc	1.0: CURRENT, Most-Recent, Effective	090032d580cd9b2d	04 Jan 2017 09:07:54
	Reason For Issue	Auto Issue		

Appendix 1 Study Schedule

Activity	Visit 1 Screening	Visit 2 Treatment Period 1	Visit 3 Treatment Period 2	Visit 4 Treatment Period 3	Visit 5 Treatment Period 4	Visit 6 Treatment Period 5
Informed Consent	X					
Demographics & Medical History	X					
Current/concomitant medication	X	X	X	X	X	X
Oral soft tissue examination	X	X	X	X	X	X
Oral hard tissue examination	X					
Plaque disclosure	X					
Plaque assessment	X					
Repeatability of plaque assessment in selection of subjects	X	X	X	X	X	X
Inclusion/Exclusion criteria	X ¹	X ¹				
Dispense wash-out toothpaste, toothbrush, countdown timer and diary card with verbal instructions	X					
Return wash-out toothpaste, toothbrush and diary card		X	X	X	X	X
Re-dispense wash-out toothpaste, toothbrush and diary card		X	X	X	X	
Pre-brushing plaque disclosure		X	X	X	X	X
Pre-brushing plaque assessment		X	X	X	X	X
Randomisation		X				
Supervised brushing with assigned toothpaste		X	X	X	X	X
Post brushing plaque disclosure		X	X	X	X	X
Post-brushing plaque assessment ²		X	X	X	X	X
Brushing with washout toothpaste to remove stain from disclosing dye	X	X	X	X	X	X
Compliance check		X	X	X	X	X
Subject Adherence/Eligibility check		X	X	X	X	X
Adverse events	X	X	X	X	X	X
Study Conclusion						X

¹ Plaque (inclusion criteria 4 C) will be assessed at Visit 1 and Visit 2; use of antibiotics and Chlorhexidine mouthwashes (exclusion criteria 7 A and 8 K) at Visit 2 to determine eligibility to continue.

 GlaxoSmithKline	Document Name	206886 SAP		
	Type	Version	Document Identifier	Effective Date
	eldo_clinical_doc	1.0; CURRENT; Most-Recent; Effective	090032d580cd9b2d	04-Jan-2017 09:07:54
	Reason For Issue	Auto Issue		

Appendix 2 List of Tables, Figures & Listings

Table No.	Table Title (including population)	Standard	Template
9.1.1.1	Subject Disposition By Treatment Group – All Screened Subjects	X	
9.1.1.2	Subject Disposition By Treatment Group and Study Period – All Screened Subjects	X	
9.1.2	Protocol Violations Leading To Exclusion From Per Protocol Analysis – ITT Population	X	
9.2.1.1	Demographic Characteristics – Safety Population	X	
9.2.1.2	Demographic Characteristics – ITT Population	X	
9.3.1.1	Analysis Of Turesky Plaque Score Change from Pre-brushing – ITT Population		App 3
9.3.1.2*	Analysis Of Turesky Plaque Score Change from Pre-brushing – PP Population		9.3.1.1
9.3.2	Repeatability Analysis Of Turesky Plaque Index – Repeatability Population		App 3
9.4.1.1**	Listing Of Adverse Events – Safety Population	X	
9.4.1.2**	Listing Of Serious Adverse Events – Safety Population	X	
9.4.2	Treatment Emergent Adverse Events By Oral/Non Oral And PT – Safety Population	X	
9.4.3	Treatment Emergent Treatment Related Adverse Events By Oral/Non Oral And PT – Safety Population	X	
9.4.4	Treatment Emergent Adverse Events By SOC And PT – Safety Population	X	
9.4.5***	Treatment Emergent Non-Serious Adverse Events By SOC And PT – Safety Population	X	

*provided only if PP analysis is done.

** If there are non AEs a NULL listing will be provided. For 9.4.1.2, if there are more than 5 serious AEs a table will be done instead of listing.

	Document Name	206886 SAP		
	Type	Version	Document Identifier	Effective Date
	eldo_clinical_doc	1.0; CURRENT; Most-Recent; Effective	090032d580cd9b2d	04-Jan-2017 09:07:54
	Reason For Issue	Auto Issue		

*** Provided only if there are more than 5 serious AEs.

FIGURES

Figure No.	Figure Title (including population)	Standard	Template
9.1	Mean Turesky Plaque Score By Treatment – ITT Population		App 3
9.2	Scatter Plot With Regression Curve Over Dose Range [0,67] (% sodium bicarbonate) – ITT Population		App 3

 GlaxoSmithKline	Document Name	206886 SAP		
	Type	Version	Document Identifier	Effective Date
	eldc_clinical_doc	1.0: CURRENT: Most-Recent: Effective	090032d580cd9b2d	04 Jan 2017 09:07:54
	Reason For Issue	Auto Issue		

Appendix 3 Templates for Tables, Figures & Listing

Treatment headers will be: Test 1; Test 2; Test 3; Positive Control; Negative Control.

For all tables add footnotes

Test 1: Experimental dentifrice containing 20% w/w sodium bicarbonate

Test 2: Experimental dentifrice containing 35% w/w sodium bicarbonate

Test 3: Experimental dentifrice containing 50% w/w sodium bicarbonate

Positive Control: Dentifrice containing 67% w/w sodium bicarbonate (German marketed Parodontax Classic (non-fluoride) Toothpaste)

Negative Control: Dentifrice containing 0% w/w sodium bicarbonate (UK marketed Macleans Fresh Mint Toothpaste - 1450 ppm Fluoride)

CCI

 GlaxoSmithKline	Document Name	206886 SAP		
	Type	Version	Document Identifier	Effective Date
	eldo_clinical_doc	1.0: CURRENT: Most Recent: Effective	090032d580cd9b2d	04 Jan 2017 09:07:54
	Reason For Issue	Auto Issue		

Protocol: 206886

Program Run Date: ddmonyyyy

Table 9.3.1.1
 Analysis Of Turesky Plaque Score Change from Pre-brushing
 ITT Population

Study Population: ITT (N=xxx)

	Test 1 (N=xx)		Test 2 (N=xx)		...	Positive Control (N=xxx)		Negative Control (N=xx)	
	Raw	Change	Raw	Change		Raw	Change	Raw	Change
Pre-brushing									
N*	XX		XX		...	XX		XX	
MEAN	X.XX		X.XX		...	X.XX		X.XX	
SD	X.XXX		X.XXX		...	X.XXX		X.XXX	
SE	X.XXX		X.XXX		...	X.XXX		X.XXX	
MEDIAN	X.XX		X.XX		...	X.XX		X.XX	
MINIMUM	X.X		X.X		...	X.X		X.X	
MAXIMUM	X.X		X.X		...	X.X		X.X	
Post-brushing									
N*	XX	XX	XX	XX	...	XX	XX	XX	XX
MEAN	X.XX	X.XX	X.XX	X.XX	...	X.XX	X.XX	X.XX	X.XX
SD	X.XXX	X.XXX	X.XXX	X.XXX	...	X.XXX	X.XXX	X.XXX	X.XXX
SE	X.XXX	X.XXX	X.XXX	X.XXX	...	X.XXX	X.XXX	X.XXX	X.XXX
MEDIAN	X.XX	X.XX	X.XX	X.XX	...	X.XX	X.XX	X.XX	X.XX
MINIMUM	X.X	X.X	X.X	X.X	...	X.X	X.X	X.X	X.X
MAXIMUM	X.X	X.X	X.X	X.X	...	X.X	X.X	X.X	X.X
ADJUSTED MEAN [1]		X.XX	X.XX	X.XX	...	X.XX	X.XX	X.XX	X.XX
SE [1]		X.XXX	X.XXX	X.XXX	...	X.XXX	X.XXX	X.XXX	X.XXX
TREATMENT COMPARISONS [1]	DIFFERENCE(CI)[1][2]				P-VALUE[1]				
Pos.Control vs. Neg.Control	X.XX (X.XX, X.XX)				0.XXXX				
Test 1 vs. Neg.Control	X.XX (X.XX, X.XX)				0.XXXX**				
Test 2 vs. Neg.Control	X.XX (X.XX, X.XX)				0.XXXX**				
Test.3 vs. Neg.Control	X.XX (X.XX, X.XX)				0.XXXX**				
Test 1 vs. Pos.Control	X.XX (X.XX, X.XX)				0.XXXX**				
Test.2 vs. Pos.Control	X.XX (X.XX, X.XX)				0.XXXX**				
Test 3 vs. Pos.Control	X.XX (X.XX, X.XX)				0.XXXX**				
Linear Contrast					0.XXXX**				
Quadratic Contrast					0.XXXX**				

*Number of subjects with non-missing values

**P-value for test products against two controls will be provided only if Pos.Control vs neg.Control is significant.

[1] From ANCOVA analysis for change from pre-brushing with treatment and period as fixed effect, subject as random effect, subject-level baseline and period-level minus subject-level baseline as covariates.

[2] Difference is first named treatment minus second named treatment such that a negative difference favors the first named treatment

(Page X of Y)

PPD

PPD

 GlaxoSmithKline	Document Name	206886 SAP		
	Type	Version	Document Identifier	Effective Date
	eldc_clinical_doc	1.0: CURRENT: Most-Recent: Effective	090032d580cd9b2d	04 Jan 2017 09:07:54
	Reason For Issue	Auto Issue		

	Document Name	206886 SAP	
	Type	Version	Document Identifier
	eldo_clinical_doc	1.0: CURRENT: Most-Recent: Effective	090032d580cd9b2d
	Reason For Issue	Auto Issue	
			Effective Date
			04 Jan 2017 09:07:54

Protocol: 206886

Program Run Date: ddmonyyyy

Table 9.3.2
 Repeatability Analysis of Turesky Plaque Index
 Repeatability Population

Study Population: Repeatability (N=xx)

First Assessment [1]	Second Assessment					
	Missing	0	1	2	3	4
MISSING	XX	XX	XX	XX	XX	XX
0	XX	XX (xx.x%)				
1	XX	XX (xx.x%)				
2	XX	XX (xx.x%)				
3	XX	XX (xx.x%)				
4	XX	XX (xx.x%)				

WEIGHTED KAPPA = 0.xxx

95% C.I. = 0.xxx, 0.xxx

Note: Percentages are based on total of all non-missing combinations

[1] The first assessment is the one used in the efficacy analysis.

0: No plaque

1: Slight flecks of plaque at the cervical margin of the tooth

2: A thin continuous band of plaque (1 mm or smaller) at the cervical margin of the tooth

3: A band of plaque wider than 1 mm but covering less than 1/3 of the crown of the tooth

4: Plaque covering at least 1/3 but less than 2/3 of the crown of the tooth

5: Plaque covering 2/3 or more of the crown of the tooth

(Page X of Y)

PPD

PPD

[figure not shown]
	Document Name	206886 SAP		
	Type	Version	Document Identifier	Effective Date
	eldo_clinical_doc	1.0: CURRENT, Most-Recent, Effective	090032d4580cd9b2d	04 Jan 2017 09:07:54
	Reason For Issue	Auto Issue		

Protocol: 206886

Program Run Date: DDMMYYYY

Figure 9.1
 Mean TPI change from pre-brushing (\pm SE) by treatment
 ITT Population

Study Population: ITT (N=xxx)

PPD

PPD

[figure not shown]
	Document Name	206886 SAP	
	Type	Version	Document Identifier
	eldo_clinical_doc	1.0: CURRENT: Most-Recent: Effective	090032d580cd9b2d
	Reason For Issue	Auto Issue	
			Effective Date
			04 Jan 2017 09:07:54

Protocol: 206886

Program Run Date: DDMMYYYY

Figure 9.2
Scatter plot with regression curve over dose range [0,67] (% sodium bicarbonate)
ITT Population

Study Population: ITT (N=xxx)

Regression curve: $TPI\ change = a + b \cdot dose + c \cdot dose^2$ from mixed effect model with dose, $dose^2$ as regressors and subject as random effect.

PPD

PPD

Document Name	206886 SAP		
Type	Version	Document Identifier	Effective Date
eldo_clinical_doc	1.0; CURRENT; Most-Recent; Effective	090032d580cd9b2d	04-Jan-2017 09:07:54
Reason For Issue	Auto Issue		

SIGNATURE PAGE

206886 SAP

Date	Signed By
03-Jan-2017 10:59:49	PPD
Justification	Biostatistics Approval

Date	Signed By
04-Jan-2017 09:07:47	PPD
Justification	Approved

Date	Signed By
Justification	

Date	Signed By
Justification	

Date	Signed By
Justification	

Date	Signed By
Justification
